### **Determination of Sample Size**

The objectives of the study are to evaluate the safety and efficacy of EQ101 and to characterise the PK [REDACTED] of EQ101 over a 24-week treatment period in adult subjects with moderate to severe AA. Though not formally powered for efficacy, the sample size of approximately 30 subjects is considered sufficient to meet these objectives.

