#### **1.4. Rationale for Study Design, Doses, and Control Groups**

This proof-of-concept (PoC) Phase 2, multicenter, single-arm, open-label study will be the first investigation of the safety and efficacy of EQ101 in subjects with AA. The objectives of this study are to evaluate the safety, tolerability, efficacy, PK, [REDACTED] for EQ101. Treatment will be weekly IV doses of the current formulation used in the previously concluded studies. This study will not include a control group given the recent completion of multiple Phase 2 and Phase 3 studies in a similar AA population that have provided historic data characterising the consistent and low placebo rates in this population. The current nonclinical toxicology studies (13-week studies completed with mice and cynomolgus monkeys) and prior clinical studies support the selected dose (2 mg/kg) and the treatment period of up to 24 weeks.

Endpoints were selected to focus on the safety and tolerability of EQ101 in this AA population, as well as PK [REDACTED] markers in order to inform on dosing for future studies and characterise the drug-response profile in subjects with AA.

Efficacy endpoints will focus on regrowth of hair by percent and absolute changes in Severity of Alopecia Tool (SALT) score and reaching improvements in SALT scores (Improvement of SALT by 50% [SALT50] and Improvement of SALT by 75% [SALT75]). Efficacy endpoints will also include measures of scalp, eyebrow, eyelash and body hair regrowth and patient-reported outcomes (PROs). The study population will be those with at least 35% scalp hair loss to focus on subjects with the greatest unmet need but have lower likelihood of spontaneous regrowth. However, the current hair loss episode must be < 7 years in order to ensure that the hair loss could be reversible.

A maximum of approximately 25% of the total study population will have AT/AU in order to assess some subjects with complete hair loss in addition to those with incomplete hair loss. Similarly, a maximum of approximately 25% of the total study population will have 35% to < 50% of scalp hair loss to ensure that this PoC study assesses subjects with different severities of scalp hair loss.

The study includes a follow-up visit approximately 4 weeks after the last administration of the study drug. This will allow blood sample collection for the assessment of PK [REDACTED] during EQ101 washout, as well as the sustainability of the clinical response.

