#### **6.7.1. SALT Score**

AA severity will be evaluated using the SALT based on scalp terminal hair loss [REDACTED]

The SALT uses a visual aid which divides the scalp hair into 4 areas with the top of the scalp representing 40% of total scalp surface area, the posterior/back of the scalp 24%, and the right and left sides of the scalp representing 18% each. The percentage of hair loss in each area is determined and is multiplied by the percentage of scalp covered by that area. The total sum of the 4 products of each area gives the SALT score [REDACTED]

Subject must have a SALT score of  $\geq 35$  at Screening and Baseline to be eligible for the study. An independent reviewer may review the photos to confirm the SALT scores.

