4.2.2.1 Efficacy

The primary efficacy endpoint is:

- The percent change from Baseline in Severity of Alopecia Tool (SALT) score at Week 24

The secondary efficacy endpoints are:

- percent change from Baseline in SALT score at Weeks 4, 8, 12, 16, and 20.
- change from Baseline in SALT score at Weeks 4, 8, 12, 16, 20, and 24.
- percentages of subjects with a SALT ≤ 20 and those with a SALT ≤ 10 at Weeks 4, 8, 12, 16, 20, and 24.

- percentages of subjects achieving 30% (SALT₃₀), 50% (SALT₅₀), 75% (SALT₇₅) and 90% (SALT₉₀) improvement of SALT from Baseline at Weeks 4, 8, 12, 16, 20, and 24.
- times to SALT score improvement of 30% (SALT₃₀), 50% (SALT₅₀), 75% (SALT₇₅) and 90% (SALT₉₀) improvement of SALT from Baseline.
- percentage of subjects achieving ClinRO Measure for eyebrow (EB) Hair Loss 0 or 1 with \geq 2-point improvement from Baseline among subjects with ClinRO Measure for EB Hair Loss ≥ 2 at Baseline at Weeks 4, 8, 12, 16, 20, and 24.
- percentage of subjects achieving ClinRO Measure for eyelash (EL) Hair Loss 0 or 1 with \geq 2-point improvement from Baseline among subjects with ClinRO Measure for EL Hair Loss ≥ 2 at Baseline at Weeks 4, 8, 12, 16, 20, and 24.
- percentage of subjects achieving ClinRO Measure for Body Hair Loss 0 or 1 with \geq 2-point improvement from Baseline among subjects with ClinRO Measure for Body Hair Loss ≥ 2 at Baseline and Week 24.
- percentage of subjects with Scalp Hair Assessment PRO of 0 or 1 with a \geq 2-point improvement from Baseline among subjects with a score of ≥ 3 at Baseline at Weeks 4, 8, 12, 16, 20, and 24.
- percentage of subjects achieving PRO measure for EB 0 or 1 with \geq 2-point improvement from Baseline among subjects with PRO measure for EB ≥ 2 at Baseline at Weeks 4, 8, 12, 16, 20, and 24.
- percentage of subjects achieving PRO measure for EL 0 or 1 with \geq 2-point improvement from Baseline among subjects with PRO measure EL ≥ 2 at Baseline at Weeks 4, 8, 12, 16, 20, and 24.
- percentage of subjects achieving PRO measure for Body Hair 0 or 1 with \geq 2-point improvement from Baseline among subjects with PRO measure Body Hair ≥ 2 at Baseline and Week 24.

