6.2 General Considerations

All data collected during the study (data originating from the electronic Case Report Forms (eCRFs) or electronic transfers will be presented in the data listings. Event-based listings will be sorted by subject identifier and event start date/time (i.e., Adverse Event (AE) start date/time). Assessment-based listings will be sorted by parameter name (alphabetically unless specifically stated otherwise), subject identifier, visit, assessment date and time (if applicable).

Unless otherwise stated, the following methods will be applied:

- Continuous variables: Descriptive statistics will include the number of non-missing values (n), arithmetic mean, standard deviation, median, minimum, and maximum values.

The minimum and maximum values will be displayed to the same decimal precision as the source data, the arithmetic mean and median values will be displayed to one more decimal than the source data, and the standard deviation (SD) values will be displayed to two more decimals than the source data for the specific variable.

The appropriate precision for derived variables will be determined based on the precision of the data on which the derivations are based, and statistics will be presented in accordance with the abovementioned rules.

- Categorical variables: Descriptive statistics will include frequencies and percentages per category. The denominator in all percentage calculations will be the number of subjects in the relevant analysis population, unless specifically stated otherwise. Percentages will be rounded to one decimal place and will not be displayed for zero frequencies.
- Repeat/unscheduled assessments: When values collected at scheduled study visits/time points is missing, repeat or unscheduled assessments closest to the scheduled visit date within the visit window defined in Table 1 and Table 2 will be used for the visit to calculate summary statistics in summary tables with visits as defined in section 6.6. All collected data will be included in the data listings. If an unscheduled visit was intended to replace the missing assessment for a scheduled visit this should be documented clearly before values are used as a scheduled visit assessment.

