6.3 Key Definitions

The following definitions will be used:

- Date of the First Study Treatment Administration: The date of the first study treatment administration is defined as the earliest date on which a study treatment was administered.
- Baseline: The Baseline value is defined as the last available valid, non-missing observation for each subject prior to first study treatment administration on Day 1. If day 1 assessment has time missing, it will be considered as the baseline.
- Change from Baseline: The change from Baseline value at each visit will be calculated for all continuous parameters using the following formula when both values are available:

$$\text{Change from Baseline Value} = \text{Result at specified visit} - \text{Baseline Value}$$

- % Change from Baseline: The % change from baseline value is defined as Change from Baseline divided by Baseline value. Study Day: The study day of an event is defined as the relative day of the event starting with the date of the first study treatment administration (reference date) as Day 1 (there will be no Day 0).

The study day of events occurring before the first study treatment administration will be calculated as:

$$\text{Study Day} = (\text{Date of Event} - \text{Date of First Study Treatment Administration})$$

For events occurring on or after Day 1, study day will be calculated as:

$$\text{Study Day} = (\text{Date of Event} - \text{Date of First Study Treatment Administration}) + 1$$

Study days will only be calculated for events with complete dates and will be undefined for events that are ‘Ongoing’ at the end of the study.

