Time to SALT score improvement of 30% (SALT₃₀), 50% (SALT₅₀), 75% (SALT₇₅), and 90% (SALT₉₀) improvement will be summarised using the Kaplan-Meier method. For the subjects who did not achieve 30%, 50%, 75% or 90% SALT Score improvement, the week of the last SALT score assessment for the subject will be treated as censoring in these analyses. If there is no post-baseline assessment, the subject will be censored at date of first dose.

Subgroup analyses: SALT score, change from baseline and % change from baseline will be summarize by these subgroups:

- 1) By Demographics (age categories (<40, >=40), sex and race)
- 2) By Site
- 3) By Baseline SALT Score Categories (<50, >=50 - < 95, >=95)
- 4) Duration of Current AA episode (<6 months, 6 months – 1 year, > 1 year - 4 years, >4 years - 7 years)

SALT Score <=20 and <=10 and 30%, 50%, 75% and 90% improvement of SALT by visit will also be summarized by baseline SALT Score Categories (<50, >=50 - < 95, >=95).

A few SALT assessments were not assessed accurately (approval status of “No”). SALT assessments were reassessed for those cases. The SALT score analysis in this SAP is based on the SALT score data with approval status of “Yes”.

For optional scalp biopsies, listing will be prepared sorted by subject identifier for the Safety population, along with age, sex, race, and baseline weight of the Subject.

For photographs for scalp, eyebrows and eyelashes and optional photographs of body hair (growth or regrowth) and fingernails, listing will be prepared sorted by subject identifier for the Safety population, along with age, sex, race, and baseline weight of the Subject.

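### Does analysing only the approved SALT scores, and adding SALT30 and SALT90 without a label, call for a change to the SAP?

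*SAP*

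**What the plan says.** SAP section 16 says a few SALT assessments carried an approval status of No because they were inaccurate. It continues: "SALT assessments were reassessed for those cases". It then sets the analysis rule: "The SALT score analysis in this SAP is based on the SALT score data with approval status of" Yes. The rule covers the primary efficacy endpoint (percent change in SALT at Week 24) and every SALT responder and time-to-response endpoint.

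Four other places bear on it:

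- SAP 6.3 defines Baseline as the "last available valid, non-missing observation for each subject prior to first study treatment administration on Day 1".
- SAP 6.2 says that data from the eCRFs or "electronic transfers will be presented in the data listings".
- Protocol 6.7.1 allows for a check: "An independent reviewer may review the photos to confirm the SALT scores".
- Protocol 6.7 requires trained SALT evaluators with standardised, documented training. Protocol 6.6.2 schedules scalp photographs at Baseline, every 4 weeks, Week 24/EOT and EOS.

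On the endpoints, protocol 2.2.3 names SALT50 and SALT75. SAP 4.2.2.1 gives percentages for 30%, 50%, 75% and 90% improvement and also "times to SALT score improvement of 30"% and the same three higher levels. All sit under one heading for secondary efficacy endpoints, with no visible note that 30% and 90% are new.

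**The concern.** The rule selects outcome data, and it was written after the re-scoring had taken place. The trial is open-label, and protocol 1.4 says "This study will not include a control group", relying instead on historical placebo data. Re-scoring errors therefore cannot cancel between arms: a run of changes in one direction would go straight into the only estimate there is. The visible text does not say whether the person re-scoring knew the visit or the first score. Summary tables built on approved scores alone cannot show how far, or which way, the scores moved.

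Baseline is the sensitive place, because it is the denominator of every percent change. SAP 6.3 does not tie the word valid to approval status. If a Day 1 score were marked No, a programmer might use the Screening score, the first Day 1 score or a later re-reading.

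SALT30 is an easier threshold than any percent-improvement level in the protocol. A good SALT30 result shown without a label could be taken as planned from the start.

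**Working it through.** The plan gives no figure to reproduce: there is no power calculation, alpha or effect size, and the number of re-scored assessments is not stated. The check is a reading of the text plus a scale calculation under stated assumptions.

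**Text.** SAP 6.3 needs a valid score for Baseline, and SAP 16 takes only scores approved Yes. Read together, a score marked No is not used as Baseline. SAP 16 says the affected cases were reassessed, so it points to no rejected score left without a replacement. If one existed at Day 1, the Baseline rule would fall back to Screening, where protocol 4.1.1 also requires a SALT score. Filtering on approval status implies that the status is held as a data field, and SAP 6.2 lists all collected data. The documents do not confirm that first scores were kept.

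**How often a key score would be touched.** Inputs: 30 subjects (protocol 3.1) and 7 analysis visits (Baseline and Weeks 4, 8, 12, 16, 20, 24), so 30 × 7 = 210 scores. Baseline and Week 24 account for 60 of them. Assume k scores re-scored at random. The expected number among the 60 is k × 60/210, and the chance that none is among them is C(150,k)/C(210,k).

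| k (assumed) | Share of 210 | Expected at Baseline or Week 24 | Chance of none |
|---|---|---|---|
| 3 | 1.4% | 0.9 | 36% |
| 5 | 2.4% | 1.4 | 18% |
| 10 | 4.8% | 2.9 | 3% |

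If Screening scores are counted too, the total is 240, and for k = 3 the chance of none is (180 × 179 × 178)/(240 × 239 × 238) = 42%. Being touched does not mean that a result changes.

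**Responder rates.** One subject is 1/30 = 3.3 points. SAP 16 promises 95% intervals without naming the method; exact (Clopper-Pearson) intervals are assumed here.

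- 6/30 = 20.0%, interval 7.7% to 38.6%, width 30.9 points.
- 7/30 = 23.3%, interval 9.9% to 42.3%.

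The shift is about one ninth of the interval width (3.3/30.9 = 0.11).

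**Mean percent change at Week 24.** If k subjects have a follow-up score moved d points in the same direction from baseline b, the mean moves by 100 × k × (d/b)/30.

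| k | d | b | Shift in mean (points) |
|---|---|---|---|
| 1 | 5 | 100 | 0.17 |
| 1 | 10 | 50 | 0.67 |
| 3 | 10 | 100 | 1.0 |
| 3 | 10 | 50 | 2.0 |
| 3 | 10 | 35 | 2.9 |
| 5 | 10 | 35 | 4.8 |

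The last row is extreme: five changes, all at Week 24, all in one direction, all in subjects at the lowest eligible baseline.

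**Baseline re-scoring.** With a Week 24 score of 27, a baseline of 50 gives (27 − 50)/50 = −46.0%, short of SALT50, while 55 gives (27 − 55)/55 = −50.9%, which meets it. It can go the other way: with a Week 24 score of 24, a baseline of 50 gives −52.0% and 45 gives −46.7%. One such subject again moves the rate by 3.3 points.

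**SALT30 and SALT90.** These are extra cut-points on the same percent change. Adding them alters neither the SALT50 and SALT75 results nor the primary efficacy endpoint. No test is attached to them, and SAP 6.4 makes no multiplicity adjustment.

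**The case for a change.** The strongest contrary case is that a selection rule on the main efficacy measure of an uncontrolled trial should carry its own evidence. A listing needs reconstruction by hand and does not show the effect on the estimate. A rerun on first-recorded scores, with a side-by-side table, would cost little and would let a reader rule out one-directional re-scoring. One sentence in SAP 6.3 and an endpoint label would cost less still.

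Part of this stands. The number, visits, reassessor and basis should be visible to a reader of the results, and the visible text does not give them. A side-by-side listing of first and final scores with approval status is the natural way to show them, with a footnote marking SALT30 and SALT90 as added in the SAP. Both are reporting steps that an analyst can take under the present SAP.

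The rest does not amount to a correction. The rerun would rest on scores the SAP itself calls inaccurate, so a difference would not show which set was nearer the truth. A rejected score with no replacement, or a Baseline reassessment dated after dosing, is a possibility that the documents do not point to. Calling SALT30 and SALT90 exploratory is a preference. Redacted parts of the SAP, and redacted text in protocol 6.7 and 6.7.1, may already cover some of this, so silence in the visible text is weak evidence of a gap.

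**Conclusion.** No change to the plan is needed. The description of the text is accurate, but following the SAP as written gives a sound descriptive result. Corrected scores are the right ones to analyse, SAP 6.3 and 16 together exclude rejected ones, and the listings rule covers what was collected. The protocol says of the sample size "Though not formally powered for efficacy", and the primary objective is safety, which this does not touch.

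Under the illustrations above, the effect is 3.3 points on a responder rate per reclassified subject, and 1.0 to 2.9 points on mean percent change for three 10-point follow-up changes in one direction. It could reach 4.8 points in the extreme case. The SALT30 and SALT90 additions change no other result.

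This rests on three assumptions: that few means roughly 3 to 10 of 210 scores, that the changes were not all large and in one direction, and that first scores were kept so they can be listed. The documents neither confirm nor contradict these. If the listings showed many one-directional changes at Baseline or Week 24, the efficacy results would need to be read with that in mind.

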17 SAFETY

All safety endpoints will be analyzed using the Safety Population.

17.1 Adverse Events

Adverse Events will be coded using the Medical Dictionary for Regulatory Activities MedDRA, Version 25.1. AEs that start during or after the first dose of study drug, or AEs with an onset prior to the first dose of study drug that worsen after study drug administration will be considered TEAEs.

Treatment-Related TEAEs are defined as any TEAEs reported with the causality of “Related” or missing to study treatment. All injection site reactions will be recorded as AE’s and will be included in the AE tables and listings.

All AE summaries will be restricted to TEAEs only.

The TEAE summaries will include:

- Overall Summary of TEAEs
 - TEAEs
 - Serious TEAEs
 - TEAEs leading to study drug withdrawal
 - TEAEs leading to study dose reduction
 - TEAEs leading to study discontinuation
 - Any Serious TEAEs leading to Discontinuation from Study
 - Any Serious TEAEs leading to Death
 - TEAEs by Severity (Grade 1 to Grade 5)
 - TEAE by Causality (Not related and Related)
 - Any Treatment-Related TEAEs
 - Severity of Treatment-Related (Grade 1 to Grade 5)
- Summary by System Organ Class (SOC) and Preferred Term (PT)
 - TEAEs
 - TEAE summary for severity level (Grade 1 to Grade 5)
 - TEAE by relationship with study drug (Unrelated versus Related)
 - Serious TEAEs
 - Treatment-Related TEAEs
 - Treatment-Related TEAEs for severity level (Grade 1 to Grade 5)
- Summary by PT
 - TEAEs
 - Treatment-Related TEAEs

The above items will be presented using summary tables, which will include the number of events and the number of subjects (%) experiencing an event. If a subject experienced the same adverse event multiple times, this will only be counted once for the purpose of counting the number of subjects experiencing that adverse event.

Summary tables will be done for the Safety population. Where SOC and PT are reported, the display will be sorted by the descending order by total counts for SOC and then by PT.

All AEs will be listed and will include the verbatim term, PT, SOC, treatment, causality/severity, date and time of consent, date and time of resolution, outcome, infusion site reaction, infusion related reaction and/or hypersensitivity reactions, action taken, discontinuation from study, SAE, TEAE, concomitant medications, additional treatment given, other action taken, worsening of medical history and the terms of the corresponding medical history, whether the adverse event associated with a congenital anomaly or birth defect, whether the adverse event result in persistent or significant disability or incapacity, whether the AE result in death, whether the adverse event result in initial or prolonged hospitalization for the patient, whether the AE was life threatening, and whether the adverse event associated with other serious or important medical events. Separate listings will be created for SAEs, Adverse Events Leading to Study Dose Reduction, Study Drug Withdrawal, and Discontinuation from study, and Infusion Site Reactions, infusion related reactions and/or hypersensitivity reactions. These listings will be presented by Subject ID and date for the Safety Population, along with age, sex, race, and baseline weight of the subject. Listing of death will be presented for the Safety Population if there was any death reported in the study.

17.2 Safety Laboratory Assessments

For the haematology, serum chemistry and coagulation, continuous data summary statistics (as described in Section 6.2) and count and percentages of normal and abnormal (defined by a test-specific normal range) will be presented for values, change from baseline at each visit.

In addition, Shift from Baseline at each visit for haematology, serum chemistry and coagulation lab parameters (low, normal, high) will also be presented using counts and percentages in shift tables.

For urinalysis and urine microscopy, continuous data summary statistics (as described in Section 6.2) and count and percentages of normal and abnormal will be presented for values at each visit.

The listings of laboratory parameters (haematology, serum chemistry, coagulation, and urinalysis) will include all the information collected. In addition, the observations that are used as the baseline record (value) for each parameter will be flagged, and the change from baseline values (where applicable) at each post baseline (scheduled and unscheduled) visit will be presented. These listings will be presented sorted by Subject ID and assessment date for the Safety Population, along with age, sex, race, and baseline weight of the subject.

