### 2.2. Study Endpoints

#### 2.2.1. Primary Endpoints

The primary endpoints of the study are:

- incidence, severity, and relationship of TEAEs, SAEs, TEAEs leading to discontinuation of study treatment;
- changes in vital sign measurements;
- changes in ECG parameters; and
- changes in clinical laboratory results.

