### **6.3.9. Clinical Safety Laboratory Tests**

Blood and urine samples will be collected for safety laboratory tests (haematology, serum chemistry, coagulation, urinalysis, and viral studies). [REDACTED]

Pre-dose safety laboratory results (i.e., haematology, coagulation, serum chemistry including LFTs, urinalysis) and those for eligibility (i.e., liver function tests) must be performed prior to Day 1 dosing.

All scheduled laboratory safety tests, unless specified, will be performed at a central laboratory.

Laboratory results will be reviewed by the Investigator (or designee). The Investigator may repeat a laboratory test or request additional tests to verify the results of the original laboratory test. In general, abnormal laboratory findings without clinical significance (based on the Investigator's judgement) will not be recorded as AEs. Laboratory values should be reported as AEs at the Investigator's discretion. When applicable, clinical sequelae (not the laboratory abnormality) can be recorded as the AE.

Detailed instructions on sample collection, processing, storage, and shipping procedures are provided in the Laboratory Manual.

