### 9.4. Statistical Analysis Methods

#### 9.4.1. Safety Analyses

AEs will be coded using the Medical Dictionary for Regulatory Activities (MedDRA) for the purposes of summarisation. TEAEs, AEs that start during or after the first dose of study drug or AEs with an onset prior to the first dose of study drug that worsen after study drug administration, will be summarised by system organ class (SOC) and preferred term (PT). Treatment-emergent serious AEs (TESAEs), TEAEs leading to treatment discontinuation, and TEAEs with an outcome of death will be summarised similarly. In addition, TEAEs will be further summarised by worst severity grade and relationship to study drug. AEs of special interest (AESI) will be summarised by SOC, PT, and worst severity grade.

Clinical laboratory data will be summarised descriptively including observed values at collection timepoints and change from Baseline. All laboratory parameters that can be graded using CTCAE v5.0 will be graded. Other safety measures including vital signs and physical examination findings will be listed and summarised as appropriate.

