4.2 Objectives

4.2.1 Primary Objectives and Endpoints

The primary objective of this study is:

The primary objective of the study is to evaluate the safety and tolerability of EQ101 in adult subjects with moderate to severe AA over a 24-week treatment period.

The primary endpoints of this study are:

- Incidence, severity, and relationship of TEAEs, SAEs, TEAEs leading to discontinuation of study treatment.
- Changes in vital sign measurements
- Changes in ECG parameters; and
- Changes in clinical laboratory results.

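### SAP 17.2 leaves urinalysis change from baseline to the listings: no change or shift summary is planned, unlike the three blood panels and contrary to Protocol 9.4.1

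*SAP*

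**What the plan says.** Protocol 6.3.9 describes collection of blood and urine for "safety laboratory tests (haematology, serum chemistry, coagulation, urinalysis, and viral studies", so urinalysis is one of the safety laboratory panels. Protocol 9.4.1 sets the analysis rule: "Clinical laboratory data will be summarised descriptively including observed values at collection timepoints and change from Baseline". Protocol 2.2.1 lists "changes in clinical laboratory results" among the primary endpoints, and SAP 4.2.1 repeats it.

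SAP 17.2 then treats the panels differently.

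- For haematology, chemistry and coagulation, continuous statistics and normal/abnormal counts "will be presented for values, change from baseline at each visit". The SAP adds "Shift from Baseline at each visit for haematology, serum chemistry and coagulation lab parameters (low, normal, high" in shift tables.
- For urinalysis and urine microscopy, the plan is continuous statistics, and "count and percentages of normal and abnormal will be presented for values at each visit". Neither change nor shift is mentioned.
- For listings: "The listings of laboratory parameters (haematology, serum chemistry, coagulation, and urinalysis) will include all the information collected". The baseline record is flagged, and change from baseline is shown, where applicable, at each scheduled and unscheduled post-baseline visit.

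SAP 6.3 derives change from baseline for every continuous parameter. SAP 6.6 includes Baseline among the visit labels for summary tables.

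**The concern.** The protocol promises that change in laboratory data will be summarised. For one panel the SAP replaces that summary with a listing and gives no reason. SAP 17.3 and 17.4 include change from baseline in their summaries of vital signs and ECG parameters, so urinalysis is out of line with the other quantitative safety data as well.

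A percentage abnormal at each visit does not separate subjects who entered with an abnormal result from subjects who developed one on treatment. The study has one arm and no concurrent control, so comparing each subject with his or her own Baseline is the main way to make that distinction. If abnormalities that appear and abnormalities that resolve are similar in number, the summary table looks flat.

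**Working it through.** The documents give no figure on this point, so there is none to reproduce. The check sets the planned outputs side by side and then asks what a by-visit table can and cannot show.

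**Step 1: planned outputs by panel (SAP 17.2).**

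| Panel | Values by visit | Change summary | Shift table | Listing with change |
|---|---|---|---|---|
| Haematology, chemistry, coagulation | yes | yes | yes | yes |
| Urinalysis | yes | no | no | yes, where applicable |
| Urine microscopy | yes | no | no | not named separately |

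**Step 2: comparison with the protocol.** Protocol 9.4.1 asks for two summaries: observed values, and change from Baseline. For urinalysis the SAP supplies the first but not the second. The protocol text shown does not mention shift tables for any panel. The departure from the protocol is therefore the missing change summary. The missing shift table is an inconsistency within the SAP.

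**Step 3: what a by-visit percentage can show.** Suppose N subjects are measured at both visits, with b abnormal at Baseline and f abnormal later. Let x be the number newly abnormal and r the number resolved. Then f = b − r + x, so the table fixes only the difference x − r = f − b. The number newly abnormal can lie anywhere from max(0, f − b) to min(f, N − b).

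Illustration: N = 30 is the approximate planned enrolment, and b = f = 3 is assumed because the documents give no rate.

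- Percentage abnormal: 3/30 = 10.0% at both visits.
- Lower limit for x: max(0, 3 − 3) = 0.
- Upper limit for x: min(3, 30 − 3) = 3.
- Share of the 30 − 3 = 27 initially normal subjects who become abnormal: 0/27 = 0% to 3/27 = 11.1%.

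The planned table is the same across that whole range. A two-by-two shift table would show x and r directly.

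**Step 4: continuous parameters.** SAP 17.2 plans continuous statistics for urinalysis, so it allows for numeric results. If the same subjects are measured at both visits, the mean change is the difference between the two visit means and can be worked out from the planned table. The spread cannot: Var(change) = s_b² + s_v² − 2ρ·s_b·s_v, where s_b and s_v are the Baseline and visit standard deviations and ρ, the within-subject correlation, is not reported. The largest individual change cannot be recovered either. If some subjects are missing at the later visit, the difference in means no longer equals the mean change.

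**Step 5: whether another output fills the gap.** Adverse event tables do so only in part. Protocol 6.3.9 says laboratory abnormalities that the investigator does not consider clinically significant are in general not recorded as adverse events. Protocol 9.4.1 also calls for CTCAE grading where a parameter can be graded, but SAP 17.2 describes no table by grade.

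**The case against.** The strongest reply is that nothing is hidden. Urinalysis is named in the listings, the baseline record is flagged, and change is given at every post-baseline visit where it applies. With about 30 subjects in one arm and no hypothesis test, a reader can find each new abnormality there. Baseline is itself a column in the by-visit table, so group movement is visible. Abnormalities that are clinically significant, symptomatic, or lead to further tests or treatment are reportable as adverse events under Protocol 6.3.1 and would reach the TEAE tables in SAP 17.1.

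Most of this stands, and it limits the point to a gap in presentation. It does not answer Protocol 9.4.1, which promises a summary, and a listing is not one. The qualifier on change in the listings also matters: categorical urine results may have no numeric change to list.

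Two further replies have some force.

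- Protocol 9.4.1 cannot be applied literally to everything in Protocol 6.3.9, because viral studies are on the same list and SAP 11.3 only lists serology. That is fair, but serology serves as an eligibility test, whereas the SAP already tabulates urinalysis at each visit.
- The protocol requires no shift table. This is correct. The case for one rests on consistency with the other panels and on its fit to normal/abnormal data.

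A reader might infer that the plan fails to deliver the primary endpoint for this panel, or that the urinalysis table would show nothing. The documents do not support either reading. The endpoint names no panel and prescribes no table, change is presented subject by subject, and the by-visit table conceals movement only to the extent that new and resolving abnormalities offset each other.

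**Conclusion.** The point holds as a minor gap. SAP 17.2 plans no summary of change or shift for urinalysis or urine microscopy. For change from baseline this departs from Protocol 9.4.1, and for both outputs it differs from the treatment of the other three panels without explanation. The by-visit percentages report net movement only. In the assumed example they cannot distinguish 0% from 11.1% of initially normal subjects becoming abnormal.

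No data are lost and no inference depends on this. The 3/30 example shows how masking can arise, and is not an estimate for this study. The urinalysis parameter list is not visible in the documents, so how many results are continuous and how many categorical is unknown. If most are categorical, the shift table is the more useful addition. If most are continuous, the change statistics are.

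**What to change.** In SAP 17.2, add for urinalysis and urine microscopy:

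1. change-from-baseline summary statistics by visit for the continuous urinalysis parameters, using the derivation already in SAP 6.3; and
2. a normal/abnormal shift-from-baseline table by visit for urinalysis and urine microscopy.

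Name urine microscopy in the listing sentence as well, so that its coverage is clear. If the sponsor prefers to leave urinalysis as it is, the SAP should state this as a deliberate difference from Protocol 9.4.1 and give the reason.

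The cost is one or two extra tables from data already collected. The existing shift table uses low/normal/high categories, so the normal/abnormal version needs a short specification of its own and cannot simply reuse the current program unchanged.
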